#### Sampling:

We will build our sampling strategy for the selection of five case study sites from the results and analysis of the Phase 1 survey, focusing particularly on the findings associated with variable 4, 'Jurisdictional contexts'. This choice is justified by our theoretical approach which gives prominence to the analysis of mutually-influencing relations between and among humans and nonhumans in identifying how impact is created in the daily work of local Healthwatch as it interacts with a range of other organisations. As Carter & Martin have discussed, 'local authority areas may not be coterminous with CCG or provider organisations' catchment; consequently some local Healthwatch must deal with multiple commissioners and providers that have different administrative and geographical boundaries' (14). The choice of focussing on variable 4 also addresses the expressed need to better understand how these relationships work in the context of the changing geographies of health promoted by STPs and moves towards integrating health and social care.

Focusing on this variable will allow us to select local Healthwatch based on the complexity of the jurisdictional context in which they operate and with whom they interact. This includes, for example, the number of health and social care providers, the number and type of organisations where local Healthwatch has formal representation (i.e. the number of Boards or Committees local Healthwatch participate in at Trusts, CCGs, local authorities), and the type of local authority (unitary or county). The exact nature and number of connections used to sample case study sites will be established on the basis of the results and analysis of the Phase 1 survey. We will select five local Healthwatch to be our organizational case studies which - taken together - provide a sufficiently wide range of examples of jurisdictional complexity to inform our overall findings and produce good practice for Healthwatch and other key stakeholders.

Healthwatch involvement Panel (HIP): We will invite 15 Healthwatch to participate in the HIP. The inclusion criteria are that they will have responded to the Phase 1 survey and indicated a willingness to

<sup>4 An earlier study of Health & Wellbeing Boards found differences in operation between those in unitary local authorities and those in county council areas (4).

participate. The exclusion criteria are that they have been selected as one of the five case study sites. In the event that we receive more positive responses than needed (n=15), we will aim to ensure maximum variation of HIP members based on the same criteria used for the sampling strategy for recruitment of case study sites.

*Interviews*: During Phase 2, we will invite Healthwatch staff, volunteers, and relevant stakeholders from the five case studies to take part in individual semi-structured interviews (12 per site; 60 in total). We will aim to interview a sample of staff, managers, volunteers, local CCG members, local authorities, local Health and Wellbeing Board members and relevant provider representatives e.g. Trust patient experience managers, patients and patient organizations who are involved in the daily work of local Healthwatch.

#### Setting/context:

Following successful recruitment of the case-study sites and before the start of the fieldwork, we will conduct a preliminary visit to each of the five Healthwatch in order to formally introduce the aims, objectives and methods of the project. We will carry out ethnographic data collection at the five selected local Healthwatch across England. We will base our observational practice in Healthwatch offices as well as accompanying the staff and volunteers to relevant daily activities and meetings (for example, visits to NHS Trusts, Health and Wellbeing boards, GP surgeries, community meetings and local authority presentations).

Data collection: we will map the everyday interactions between the five local Healthwatch and a range of actors including local authorities, citizens, Trusts, CCGs, and charities. An ANT approach will allow us to attend to the socio-material environments (documents, reports, data and funding) that shape the interactions between individual and institutional actors (1). We will collect 3 forms of data:

- ethnographic fieldnotes (nine 3-days visits at each site; total 135 days) e.g. attending meetings; accompanying staff and volunteers on data gathering, outreach and inspection activities; attending training and observing the daily work in offices.
- individual semi-structured interviews (12 per site; 60 in total; 60-90 minutes each) with employed staff of all levels, volunteers, CCG members, Health and Wellbeing Board members, local authorities and relevant provider representatives e.g. Trust patient experience managers, patients and patient organizations.
- documentary evidence such as internal documents, reports, Health and Wellbeing Board minutes, local Healthwatch and Healthwatch England strategy documents.

At each local Healthwatch, we will identify key interactions between human and non-human actors and observe the practices in which these interactions are embedded. As part of our ethnographic work, we will record our observations of office work, meetings, the production and circulation of reports, the collection of data, everyday interactions between Healthwatch members and external actors such as the CCG, local GPs, Health and Wellbeing Board, patient experience and engagement managers at Providers. The role of social care commissioning and provision in our study of local Healthwatch will be considered as it arises in the observed work of the five local Healthwatch selected as case-study sites (and among the additional 15 Healthwatch that form the HIP). For instance, how and why might a local Healthwatch's focus on issues of social care commissioning and provision? What examples are there of Healthwatch engaging in social care commissioning and provision and what are the implications of this for their operation and effectiveness?

We will pay equal attention to interactions between human and nonhuman actors (for example, strategy documents, funding applications, data, 'Enter and View' reports) as they take place and produce effects.

Observational data will be recorded as written fieldnotes. Occasional still photographs will be taken of meetings and daily activities. In each of our five case study sites we will also carry out individual semistructured interviews with a range of local Healthwatch staff and volunteers, CCG members, Trust staff, Health and Wellbeing Board members, local authority officers. This will enable us to explore themes that emerge through the other two forms of data collection (non-participant observation and documentary evidence), as well as elicit opinions from research participants, test hypotheses, and obtain targeted information.

The discussions of emerging findings at 5 half-day meetings with the Healthwatch Involvement Panel (HIP) during phases 2 and 3 will be minuted to serve as a record of proceedings and enable data analysis. These meetings will take place on King's College London premises or online.

#### Data analysis:

Data from documents, interviews, observations and still photographs will be triangulated to develop detailed descriptions of the daily work, relationships and strategies of the five local Healthwatch case study sites. These data sources will provide both contextual information and specific insights into how local Healthwatch creates influence in their daily interactions with key actors. ANT is primarily concerned with giving equal analytical prominence to the relations between and among nonhumans as well as humans; that is, the way in which people and objects shape each other through ongoing mutual relations. In interrogating our ethnographic data, we will prioritise and foreground the detailed, contextualised description of interactions and relations between various actors (both human and nonhuman) that constitute the work of local Healthwatch. We will generate topical word codes, which will have an indexing function as the ethnographic work progresses through Phase 2, and thus help us to order our analytical framework. The codes will consist of key words, concepts and ideas, some of which may be 'in vivo' i.e. provided by research participants themselves. We will place codes at the top of fieldnote entries and at appropriate points in the text as they are written at the time of fieldwork; these will be refined as fieldnotes are read and re-read during data analysis. Likewise, codes will be attached to interview transcripts and documentary material. Case-study site researchers will conduct case-bycase analysis; cross-site analysis will be conducted at study team meetings and in collaboration with the Healthwatch Involvement Panel (HIP).

Data analysis will be an iterative process alongside data collection and will include 5 half-day meetings with the HIP. In advance of the first data analysis meeting, HIP members will attend a one-day training session on ethnographic data collection and analysis run by AD and GZ and facilitated by the HIP Chair SB. At each HIP meeting, data from case-study sites will be presented using a PowerPoint presentation by the research staff conducting the ethnographic fieldwork. HIP members will be asked:

- to reflect on the data presented and provide interpretation and explanation based on their own experience and knowledge of working at a local Healthwatch;
- to look for points of similarity and difference with their own organisational practices to help build a broader picture of local Healthwatch activity across England;
- to guide the research team with detailed suggestions on how to develop the ethnographic work in accordance with short and medium-term fieldwork objectives.

The core purpose of the HIP is to provide the basis for ensuring the ongoing generalisability of our findings.

# Phase 3: online interviews and small-group discussions with HIP members to generate emerging statements of good practice (and lessons emerging from COVID-19 pandemic)

Sampling: 15 members of the HIP (representing 15 local Healthwatch which are not case study sites for ethnographic fieldwork in phase 1).

#### Setting/context: online/telephone interviews

Data collection: Online interviews and small-group discussions will be arranged with HIP members. For small-group discussions, we will hold online meetings for groups of 3-5 members. Based on our phase 2 findings we will create statements of good practice which we will discuss and refine through an iterative process with HIP members and through the JIFs (see phase 4 below). These statements will be generalisable though they will not all apply equally to all Healthwatch. With the help of the HIP members we will seek to advise on contexts where they might apply and work best. These statements of good practice will not necessarily be linked to the COVID-19 pandemic (although the pandemic has highlighted and catalysed existing practices and relationships which may well constitute examples of 'good practice'). We will therefore ask HIP members questions relating to the local management of the pandemic and the work and role of local Healthwatch during this time. Researchers will take notes during these sessions. Online sessions will also be recorded and transcribed by our approved transcriber.

Data analysis: We will read session transcripts and our fieldnotes. We will generate topical word codes, which will have an indexing function across the interviews and thus help us to order our analytical framework. The codes will consist of key words, concepts and ideas, some of which may be 'in vivo' i.e. provided by research participants themselves. We will place codes at the top of fieldnote entries and at appropriate points in the text as they are written at the time of our interviews; these will be refined as fieldnotes are read and re-read during data analysis. Likewise, codes will be attached to interview transcripts and documentary material. Analysis across the interviews and small-group discussions will be conducted at study team meetings and in collaboration with the Healthwatch Involvement Panel (HIP).

#### Phase 4: Joint Interpretive Forums (JIFs)

Joint Interpretative Forums (46) will engage multiple stakeholders in joint reflection and interpretation of findings from phases 1, 2 and 3. A cross-site JIF with key stakeholders from the five case study sites and national policy makers and representatives from patient organisations will take place in London or online to enable cross-sites exchanges and dissemination. This will be followed by local JIFs conducted with individual study-sites and their particular stakeholders. This will take place at the study-site or online.

[figure not shown]
Sampling: Participants in JIFs at each case-study site locality will comprise local Healthwatch staff and volunteers, CCG members, local authority officials, Health and Wellbeing Board members, GP surgeries, Trust staff involved in patient experience and engagement, citizens and patients, relevant members of local CLAHRC, with the addition of policymakers for the cross-site JIF. These will have been purposively identified on the basis of their involvement in networks associated with local Healthwatch and their willingness and availability to participate. We will aim to involve 8 participants at each case-study JIF (of which 2 participants are patients or public) and 16 participants at the cross-site JIF (of which up to 10 will be key stakeholders from case study sites).

Setting/context: The initial cross-site JIF will be held in London or online and will involve representatives from all case study sites as well as policy makers and representatives from patient organisations. One JIF will then be held at each of the five case-study sites selected for the ethnographic work in phase 2 or online. Each JIF will last no more than two hours.

Data collection: At each JIF, members of the research team will present the background to the study and the findings from Phases 1, 2 and 3. The participants at this JIF will be asked to interpret verbally the emerging statements from Phase 3 with the aim of converting them into principles of good practice for local Healthwatch. Discussion will be facilitated by one member of the study team. The proceedings of each JIF will be audio-recorded and transcribed.

Data analysis: JIF transcripts will be analysed thematically with the specific purpose of developing practical and generalizable recommendations for policy and practice to optimise patient and public voice in NHS commissioning and service provision.

# 5.2 Flowchart

Protocol version 2.0

# 6. Subject selection

Participants will be selected based on their association with five local Healthwatch study sites. See 'Sampling' sections above for further details.

# 6.1 Subject inclusion criteria

Staff and volunteers of local Healthwatch organisations in England

NHS staff, patients/carers, adult social care users (all over 18 years), and local residents who engage with local Healthwatch organisations in England and are able to give informed consent.

Staff of non-Healthwatch, non-NHS organisations such as employees of local authorities, third-sector bodies, Health and Wellbeing Boards, who have working relationships with local Healthwatch.

# 6.2 Subject exclusion criteria

Patients/carers/social care users (under 18 years) who engage with local Healthwatch organisations in England

Patients/carers/social care users of any age unable to give informed consent

# 7. Study procedures

# 7.1 Subject recruitment

### Healthwatch staff:

With sensitivity to the work demands of staff, researchers will identify practices to observe at each case study site and which staff to interview at which site. Researchers will establish, through informal conversations with members of staff in managerial as well as front-line roles, which practices to observe and who to invite for semi-structured individual interviews. The researchers will also identify, in consultation with staff, those routine group practices that might be still photographed.

Potential participants will be approached by a member of the research team or by a member of staff who will then inform the researcher of this member of staff's interest in the study. At this time the researcher will briefly explain the study to that individual, invite and answer any questions and give them the Healthwatch Staff Participant Information Sheet. Brief contact details (e.g. work mobile number) may be requested only from that individual and only if it is not possible for the researcher and individual to plan appropriate times for data collection personally. Not less than 48 hours later the researcher will contact that member of staff again to check their continued interest, to request and answer any further questions about the research or the interview, and to arrange a suitable interview place and time. Researchers from the team will have sole responsibility for providing detailed information about the study and ensuring that potential participants are aware and informed of the study.

# NHS staff, employees of other organisations and patients/carers/social care users who have engaged with local Healthwatch:

The approach will first be by a member of the local Healthwatch team who has previously been in contact with the potential participant and who will ask them if they are happy for their details to be passed on to the researcher. Potential participants will be identified in liaison with appropriate Healthwatch staff. The appropriate Participant Information Sheet will be given to the potential participant when their initial interest in the study has been established in a short, face-to-face, conversation with the researcher. The researcher will allow at least 48 hours between giving the participant information sheet and contacting the participant. At this contact the researcher will check that the potential participant is still interested in participants' role within it.

Researchers will always seek informed consent for group observation or interview.

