### Consent for Healthwatch, NHS staff, employees of other organisations' semistructured interviews:

Consent will be signed for by that member of staff on the research participant consent sheet. It will be explained to participants that they can withdraw their consent to interview prior to and during the interview even though they have signed the consent form. Where interviews take place over the telephone/online, the researcher will audio-record - with permission - the consent procedure over the telephone/online. Participants will be able to decline audio-recording of the interview, at any point during the interview, even though the consent procedure is recorded.

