### **Consent for patient/social care user semi-structured interviews**

Consent from patients will be obtained from patients/social care users/carers who have engaged with Healthwatch following a careful information-giving process involving at least two contacts with the researcher, with 'opt out' available to patients at each stage of this engagement. Prior to obtaining consent, the researcher will check that the patient/social care user/carer understands the study and their part within it and will ask for and answer any questions that the potential participant may have concerning the study and their role within it. Consent will be obtained only by the named researcher and, wherever possible, this researcher will be the same researcher who engages with the participant throughout the recruitment process. Consent will be obtained immediately prior to participant interview. It will be explained to the participant that they can withdraw consent prior to, and at any time during, the interview irrespective of their signing the consent form.

In the case of face-to-face interview, consent will be established in writing by the patient consent sheet. Where interviews take place over the telephone or online, the researcher will audio-record - with permission - the consent procedure over the telephone/online. It will be explained to these participants that they will be able to decline audio recording of the interview, at any point during the interview even though the consent procedure is recorded.

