# 8.1 Safety of participants

Patients, carers, adult social care users and members of Healthwatch, NHS and other organisations' staff will be asked about their experiences of interacting and working for local Healthwatch organisations. They will not be asked about intimate or potentially distressing care or work place experiences. However, the following steps will still be in place to minimise the risk of distress:

1. Interviews, as well as all informed consent processes, will be carried out only by named and experienced researchers from the study team. Both the researchers are highly experienced in interviewing patients on sensitive and less sensitive research topics. They are also all experienced in offering as well as seeking support for interviewees should the interview event caused distress.

2. Should a participant become distressed during interview or observation participation, the researcher will stop the procedure and recommence only if/when the participant tells them that they are comfortable to continue.

3. We will ensure the availability of information on local NHS systems and personnel for the provision of expert support (e.g. from local Patient Advice and Liaison Service).

4. Joint Interpretive Forums (JIFs) involving Healthwatch, NHS and other organisations' staff, and patients and carers may also trigger group dynamics proving uncomfortable for some. In view of the topics to be discussed at JIFs, this is unlikely, however. JIF discussions will be facilitated by members of the research team, all of whom are experienced in the management of complex group dynamics and the minimisation of possible participant distress. Furthermore, advice will be sought from the advisory group, and its patient/carer members in particular, on how to best prevent and/or handle potential tensions in the groups.

The burden of research time for Healthwatch, NHS and other organisations' staff involved in the study will be minimised by the following:

1. Interviews with staff will be organised flexibly and outside of most pressured work periods.

2. Interviews will be conducted in private areas that are close to routine work (eg. usual offices or quiet rooms)

3. An option for telephone/online interview will be offered.

4. Interviews will not exceed 90 minutes (and are likely to be 45 minutes for most staff)

5. Opportunity to participate in observation research (comprising minimum research time burden) will be available without staff interview participation.

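### External interviewees must talk to the researcher face-to-face before they receive the information sheet, so the remote interview and consent options cannot be used by anyone who does not first meet the researcher in person

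*Protocol*

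**What the plan says.** **Recruitment of people outside Healthwatch (section 7.1).** A Healthwatch member opens the route: "The approach will first be by a member of the local Healthwatch team who has previously been in contact with the potential participant". The researcher comes second. The information sheet is handed over when the person's initial interest "has been established in a short, face-to-face, conversation with the researcher". The researcher then waits at least 48 hours before making contact again.

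**Recruitment of Healthwatch staff (section 7.1).** Here "Potential participants will be approached by a member of the research team or by a member of staff who will then inform the researcher" of the person's interest. The text continues: "At this time the researcher will briefly explain the study to that individual", after which questions are answered and the sheet is given. No mode of contact is stated.

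**Consent and interview (section 7.2).** At least 48 hours with the sheet must pass before written consent to interview is sought. For Healthwatch staff, NHS staff and employees of other organisations: "Where interviews take place over the telephone/online, the researcher will audio-record - with permission - the consent procedure over the telephone/online". For patients, social care users and carers: "Where interviews take place over the telephone or online, the researcher will audio-record - with permission - the consent procedure over the telephone/online".

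**Burden on staff (section 8.1).** Among the measures to limit research time for Healthwatch, NHS and other staff: "An option for telephone/online interview will be offered".

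**Elsewhere.** The current version is dated 29 September 2020 (section 3). Section 5.1 lets the Healthwatch Involvement Panel meetings and the Joint Interpretive Forums be held online, and Phase 3 is conducted online or by telephone.

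**The concern.** The protocol accepts that an external participant may be interviewed, and may consent, without being in the same room as the researcher. It does not accept that the same person may be introduced to the study that way. The restriction sits at the start of the chain, so it governs everything after it. A commissioner or patient for whom the remote option matters most is the one least able to use it.

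This is a rule the protocol states, not a detail left open. It is stated only for people outside Healthwatch. Objective 2 (section 4.3) is to assess the impact of local Healthwatch on commissioning and provision, and the views of commissioners, providers and patients are a check on Healthwatch's own account of its influence. If the in-person step put some of them off, the interview evidence would lean towards that account.

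**Working it through.** No sample-size or power formula applies. Phase 2 is qualitative and has no powered target. The check is whether the provisions can be followed together, and whether the size of any effect can be derived.

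**1. The plan's own figures (section 5.1, Phase 2).**
- Interviews: 12 per site × 5 sites = 60. Reproduced. Section 3 words the same figure as a maximum.
- Fieldwork: 9 visits × 3 days × 5 sites = 135 days, or 9 × 3 = 27 days per site. Reproduced.

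**2. The chain for an external interviewee.**
- Healthwatch member makes the approach (7.1).
- Face-to-face conversation with the researcher (7.1).
- Information sheet given (7.1).
- At least 48 hours (7.1 and 7.2).
- Consent and interview, in person or by telephone or online (7.2; for staff also 8.1).

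Without the conversation there is no sheet, and without the sheet there is no interview. The remote options at the last step are therefore open only to people who have already met the researcher in person.

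**3. Could face-to-face include a video call?** Not comfortably. The patient consent text in section 7.2 treats a face-to-face interview (signed consent sheet) and a telephone or online interview (recorded consent) as different things.

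**4. Comparison with Healthwatch staff.** Their text in section 7.1 contains no face-to-face condition, but it is silent on mode rather than permissive. Handing over the sheet, and asking for contact details only when times cannot be arranged personally, suggest that in-person contact was expected there too. The difference is that the condition is written down for one set of people and not for the other.

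**5. Can the effect be sized?** No. The protocol gives no refusal or loss rate and no number of interviews per stakeholder group. The table is purely illustrative: E is the assumed number of external interviewees among 12 per site, and L is an assumed fraction of them lost and not replaced. External share after loss = E(1 − L) / [E(1 − L) + (12 − E)].

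| E per site (5 sites) | Share, no loss | L = 10% | L = 50% |
|---|---|---|---|
| 4 (20) | 4/12 = 33% | 3.6/11.6 = 31% | 2/10 = 20% |
| 6 (30) | 6/12 = 50% | 5.4/11.4 = 47% | 3/9 = 33% |
| 8 (40) | 8/12 = 67% | 7.2/11.2 = 64% | 4/8 = 50% |

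The shift runs from 2 or 3 percentage points to 17. Where it lies depends wholly on the assumptions, and it is zero if each lost interviewee is replaced by another external one.

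**The case against.** The best reply is that the steps are sequential and can both be obeyed. A board member met at a meeting can be interviewed by telephone weeks later. Section 7.2 expects at least two researcher contacts with patients without fixing their mode, section 8.1 concerns only the interview and only staff, and nothing promises that a Phase 2 interviewee may take part wholly remotely. A personal introduction is also a defensible consent safeguard. This stands as far as it goes: the provisions are not strictly contradictory. It does not explain why a person whose remote consent is acceptable must first be met in person.

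The design also supplies opportunities to meet. Over 135 fieldwork days researchers accompany Healthwatch to Trusts, Health and Wellbeing Boards, GP surgeries and community meetings. That stands for regular contacts; it helps less with patients or stakeholders who are seldom present.

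External voices have other routes as well. Group observation needs no prior one-to-one meeting, and the forums, which may be online, are joined through advance information and voluntary participation. That stands in part: the forums interpret findings already produced, and section 3 says some of their members will be interviewees.

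Three stronger readings are tempting and are not supported:
- *That external interviewees are being lost.* No loss is documented, and the protocol does not say how many interviews were outstanding in September 2020.
- *That Healthwatch staff may be recruited remotely.* Their text is silent on mode.
- *That most of the sample is affected.* Section 5.1 lists 9 interviewee groups in one place and 8 in another, 6 of them external each time. Spreading interviews evenly over groups gives 12 × 6/9 × 5 = 40, or 12 × 6/8 × 5 = 45, of 60 (67% to 75%). The even spread is an assumption, and the result measures exposure to the rule, not loss or bias.

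**Conclusion.** The point holds as an avoidable restriction. Section 7.1 makes a face-to-face conversation the condition for receiving the information sheet for everyone outside Healthwatch, and with the 48-hour rule this closes wholly remote participation in interviews to them, although sections 7.2 and 8.1 accept remote interview and section 7.2 accepts recorded remote consent. It may selectively deter the people whose views objective 2 needs. The direction is inferred from the condition being stated for external groups only, and the size of any effect on sample balance is unknown. The conclusion rests on reading face-to-face as in person, which section 7.2 supports. This is a cheap improvement worth making, not a flaw that undermines the study.

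**What to change.** In section 7.1, under the heading for NHS staff and others who have engaged with Healthwatch, let initial interest be established *in a short conversation with the researcher, face-to-face, by telephone or online*. Add that the information sheet may be sent electronically or by post. Keep the interval of at least 48 hours.

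The cost is one sentence, a short addition and a minor amendment, with no extra staff. The downside is slightly less rapport at first contact. Recording the mode of first contact by participant group is optional; it would let the final report describe who was reached and how.
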